4.1 Subject Benefit

The study is a crossed randomized control study of metabolites from the gut microbiota and every patient enrolled in the study will receive free use of intestinal probiotic metabolites. The study will provide the relevant test, nutrition and quality of life evaluation free of charge. The examinations in the study are all routine examinations in daily clinical work and do not increase the burden of blood collection for patients. The only invasive test is venous blood sampling for urotoxins measurement, which is carried out according to the routine procedure. The patient needs to collect a stool sample for microflora measurement. The other tests and evaluations are non-invasive.

Regular treatment will not be affected for the patients who do not accept the study. The privacy information of all patients entering the study will be protected and the data will be used in accordance with relevant regulations.

4.2 Subject Risk

During the trial, the treatment group will take 150ml of Yi En Yuan honey yeast drink each day. The product is made of water, edible brown sugar and honey. It's mixed fermented by plant lactic acid bacteria and Bacillus coagulates and sterilized at a high temperature. The product is produced according to GB7101 standard, and there is no live bacteria and prohibited ingredients in the product, which meets the food and beverage standards. According to *NJ-W22070721 Yi En Yuan honey yeast drink* and *SH-W23040315 Honey enzyme beverage test report*, the product includes carbohydrate 4.0-4.7g/100mL, potassium about 60.9mg/100mL, phosphorus about 2.8mg/mL. According to the concentration shown above, if you consume 150ml of the product a day, you will intake carbohydrate 6.0-9.1g, potassium 90mg, phosphorus 4.2mg, which is far lower than the daily intake of these substances from the diet and can be used for dialysis and diabetic patients. Since its launch in June 2021, no side effects have been reported. Patients in the control group will be given 150ml of placebo each day which is made of water and food coloring.

Blood samples of the subjects are taken at the same time as routine clinical tests without additional samples. The risks are the same as those in daily blood drawing tests, including puncture pain, the need for a second puncture when the blood drawing is not successful, and a small amount of subcutaneous bleeding caused by poor compression after blood drawing. Blood drawing will be performed by experienced nurses. The venous blood collection routine will be strictly followed, and after blood

collection we will press effectively to stop bleeding. If the puncture is unsuccessful, we will stop the second puncture and we will try again after 24 hours.

4.3 Confidentiality

This study mainly collects the required data before and after treatment for efficacy observation. Personal data in the study are confidential. The blood samples are routine clinical laboratory items, and all are daily clinical work. The laboratory department will handle them according to the routine clinical laboratory. Researchers are required to keep the identity of the subjects confidential. Clinical data and records of the subjects will be kept in a locked filing cabinet and will be accessible only to the investigator. No personal data is disclosed at publication. There are no potential conflicts of interest and no special people involved in this study. The personal data of the subjects in the study will be confidential, and their blood samples will be coded by a unique number rather than their name. No identifying information will be disclosed to anyone other than the researchers, and all researchers are required to keep their identities confidential. In order to ensure that the study is carried out in accordance with the regulations, members of the government management department or the ethics committee can access the personal data of the subjects if necessary, and the process will also strictly follow the principle of confidentiality. No personal information about any subjects will be disclosed when the results of this study are published.

5. Quality Control

5.1 Quality Control of Clinical Research Process

Clinical data collection will be performed by the clinicians. The clinicians participating in this study must have received relevant training and understand

thoroughly about the objectives and procedures of the research. Besides, they should be able to collect high-quality clinical data and biological samples and then pass them to the data analysts and laboratory testers after preliminary collation and store. In the process, they should ensure the rights and interests of the subjects. Each subject will be numbered individually by the clinicians in order to protect their privacy and conduct blind analysis. The data of each subject will be verified by two clinicians to ensure authenticity and reliability.

5.2 Laboratory Process

1) Collection of blood and stool sample: Stool samples will be collected by the subjects themselves, and the fresh stool should be 5ml within 2 hours after defecation. Blood samples will be collected by the nurses, and 5ml of venous blood before dialysis is taken from the subjects on the same day.

2) Packaging and testing of blood and stool samples: After checking the subject number, the specimens will be immediately packaged and stored in the -80 °C refrigerator. The samples will be tested by professional laboratory technicians. Levels of urotoxins will be detected with commercial kits, requiring two multiple holes setting up in each sample with four-parameter Logistic regression method to fit the standard curve with $R^2 \geq 0.99$. Quality control products will be set up for quality control in each test. After preliminary sorting, the test data will be encrypted, stored and backed up for the data analyst.

5.3 Quality Control of Data Management

Part of the data collection will be carried out by trained nurses, and the entry and post-entry verification will be carried out by different personnel. Among the observation indicators involved in the study, the clinical laboratory test results will be uploaded to the database after completion. The electronic medical record system of

the hemodialysis center has a database interface, which can automatically extract and export to the document without manual input process. Statistical principles will be strictly followed to ensure the authenticity of the results, and the results will be interpreted and discussed with the study designers.

5.4 Training

The questionnaires and scores involved in the study, such as quality of life and malnutrition scores, will produce quantitative assessment data, and the specific operation process may affect the results. Therefore, there are specific and complete standardized operation procedures for the operation process of the above scales, and there are special trainings for researchers involved in the evaluation as well.

9.1 Appendix A. SGA 7 Scale

SGA 7 Scale: 6-7 points are classified as very mild malnutrition to good nutrition; 3-5 points are classified as mild to moderate malnutrition; 1-2 points are classified as severe malnutrition.

Subjective Comprehensive Nutrition Assessment Form

Items	Instructions	Score
-------	--------------	-------

Change of Weight (Measured in % compared to the weight 6 months earlier) Dry weight 6 months ago: ___Kg Dry weight 2 months ago: ___Kg Current dry weight: ___Kg	+5% is normal 7 points: Body weight stable without change 6 points: There is a recent trend of weight loss >5 to 10% indicates a potential problem 5 points: Weight loss of 5 to 6% 4 points: Weight loss of 7-8% 3 points: Weight loss >10% >10% indicates serious problems 2 points: Weight loss, recent tendency to stabilize or slight change 1 point: Sustained weight loss	
Diet Based on daily intake of the patients and evaluate whether it meets the dietary recommendations	7 points: Normal amount 6 points: Decreased in recent days, but usually moderate 5 points: Continuous reduction, but moderate 4 points: Continue to decrease, sometimes moderate and sometimes not 3 points: Continued to decrease, but not a moderate amount 2 points: Continued to decrease, mostly very little food 1 point: Continued to decrease, but very little food	
Gastrointestinal Symptoms Loss of appetite, nausea, vomiting, diarrhea, etc. The frequency and duration of symptoms.	7 points: Asymptomatic 6 points: Symptoms are rare 5 points: One or more symptoms occur, but not daily 4 points: Appear more than one per day 3 points: Most symptoms appear daily 2 points: A day with almost all symptoms 1 point: Daily occurrence of all symptoms	
Ability of Daily Living (Compared to 6 months ago) Work, family, social	7 points: General condition 6 points: Worse than average, but not related to nutritional status 3-4-5 points: Worse than average, but related to nutritional status 2 points: Bedridden or wheelchair, related to nutritional status but can perform simple activities 1 point: bedridden, related to nutritional status but unable to perform simple activities	
Metabolic Stress	7-6 points: Only ESRD or (and) well-controlled DM 4-5 points: DM with infection/fever/peritonitis/poor control 1-2-3 points: Serious diseases such as ulcerative colitis with diarrhea	
Physical Examination Measure muscle layer and fat layer	1 point (sunken) - 7 points(full) fat: eyelids/triceps/biceps 1 point (bone protrusion) - 7 points (bone not easily seen) Muscles: temples/scapula/clavicle/ribs/jaws and interphalanges of palms/quadriceps/knees 1 point (severe edema) - 7 points (no edema) : Edema of fibula or ankle	
Total	Do not average; Overall nutritional status and clinical experience are evaluated to range from 1 to 7 points.	

The result is shown as follows:

Items	Score						
Change of Weight							
Diet							
Gastrointestinal Symptoms							
Ability of Daily Living							
Metabolic Stress							
Physical Examination	
 
 Fat		
 
 Muscle		
 
 Edema		
 
	Fat		Muscle		Edema	
Fat							
Muscle							
Edema							
Total							

Physical Examination of Fat and Muscle:

Fat: Eyelids, triceps, biceps. 1 point is classified as sunken; 7 points are classified as full.

Muscle: temples, scapula, clavicle, ribs, jaws and interphalanges of palms, quadriceps, and knees. 1 point is classified as bone protrusion; 7 points are classified as bone not easy seen.

Researchers should give an overall score (from 1 to 7) refer to the combination of fat and muscle assessment and the final average should be rounded.

Change of Weight of 6 Months:

Body weight stable without change: 7 points.

Weight loss less than 3%: 6 points.

Weight loss of 3-5%: 5 points.

Weight loss of 5-7%: 4 points.

Weight loss of 7-10%: 3 points.

Weight loss of 10-15%: 2 points.

Weight loss more than 15%: 1 point.

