3.1 Design

The study is a multicenter prospective open labeled randomized controlled trial. Elderly patients with age ≥ 65 years and received hemodialysis treatment for more than 6 months will be included in the study. After enrollment, the patients will be educated about how to keep diet records and then they will be randomly divided into group A and group B in a 1:1 ratio. The patients in group A will receive oral postbiotics and group B receive placebo. The treatment period is 12 weeks. Subsequently, group A ends the trial, and group B enters the remedial treatment period, receiving oral postbiotics, and the treatment cycle is 12 weeks. At 0, 12th and 24th week, quality of life score, nutrition evaluation, diet status and gastrointestinal symptom score of patients will be evaluated. The stool and serum of patients will be collected for intestinal flora and urotoxins IS, PCS and TMAO measurements. The improvement of biochemical indicators will be evaluated. The biochemical indicators include blood creatinine, urea nitrogen, albumin, prealbumin, hemoglobin, blood calcium, blood phosphorus, whole parathyroid hormone, blood potassium, C-reactive protein, ferritin, transferrin saturation, et al. During the whole intervention process, patients will be encouraged to maintain intake of protein and fiber and keep a diet log.

During the intervention process, the process of hemodialysis and other diagnosis and treatment behaviors will be performed according to clinical routine.

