3.4 Outcomes

3.4.1 Primary Outcome Measure:

Outcome Measure	Measure Description	Time Frame
Changes of nutritional status from the baseline to the end of treatment and differences between the intervention group and the placebo group.	Nutritional status of the patient is defined as the results of physical examination and SGA-7 rating scale.	From the baseline to the end of treatment.
Changes of quality of life from the baseline to the end of treatment and differences between the intervention group and the placebo group.	Quality of life of the patient is defined as the scores of gastrointestinal symptom rating scale (GSRS), kidney disease life quality scale (TM-SF36) and enervation frailty scale (EFS).	From the baseline to the end of treatment.

3.4.2 Secondary Outcomes:

Outcome Measure	Measure Description	Time Frame
Changes of enterogenous urotoxin level from baseline to the end of treatment and difference between the intervention and placebo group.	Enterogenous urotoxin level is defined as the serum level of IS, PCS and TMAO. The levels of serum IS, PCS and TMAO will be measured by mass spectrometry.	From the baseline to the end of treatment.

Changes of intestinal flora structure from the baseline to the end of treatment, and the difference between the intervention group and the placebo group.
	
The structure of intestinal flora will be measured by the V3-V4 region of 16S rDNA with MiSeq PE300 sequencing platform for high-throughput analysis and described by number of the flora.
	
From the baseline to the end of treatment.

Changes of routine biochemical indicators from the baseline to the end of treatment, and differences between the intervention group and the placebo group.
	
The routine biochemical indicators include serum creatinine, urea nitrogen, albumin, prealbumin, hemoglobin, serum calcium, blood phosphorus, total parathyroid hormone, serum potassium, carbon dioxide, C-reactive protein, ferritin, transferrin saturation.
	
From the baseline to the end of treatment.

Changes of dietary intake from the baseline to the end of treatment, and the difference between the intervention group and the placebo group.
	
Dietary intakes of the patients will be described by the diet record.
	
From the baseline to the end of treatment.

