9.4 Appendix D. Enervation Frailty Scale (EFS)

Score: _____ /17				
		0 Point	1 Point	2 Points
Clock test (cognition)	1. Think of this pre-drawn circle as a clock. 2. Write the number down on the dial in the correct position. 3. Put the pointer in the "eleven ten" position.	No mistake	Mild mistake	Other mistake
General health state	How many times did you hospitalize in the past year?	0	1-2	>2
	How would you describe your overall health?	Very good & Good	Normal	Terrible
Functional independence	How many of the following activities do you need help? (Cooking, shopping, transportation, phone calls, housework, laundry, financial management, medication)	0-1	2-4	5-8
Social Support	When you need help, do you think there will be someone willing to help and able to meet your needs?	Often	Sometimes	Never
Medication	Do you take 5 or more pills a day?	No	Yes	
	Would you forget to take medicine?	No	Yes	
Nourishment	Did you lose any weight recently, such as your clothes becoming looser?	No	Yes	
Emotion	Do you often feel depressed?	No	Yes	
	Do you have trouble in controlling urinating when you don't want to urinate?	No	Yes	
Somatic function	Sit in the chair with your back and arms relaxed. Then, when I say "go," stand up and walk at a safe and comfortable pace to the mark on the floor (about 3 meters away), then return to your chair and sit down.	0-10s	11-20s	More than 20s, or unwilling to act, or need assistance to act

Evaluation: 0-5 points are defined as not weak; 6-7 points are defined as vulnerable; 8-9 points are defined as mild weakness; 10-11 points are defined as moderate weakness; more than 11 points are defined as severe weakness.

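### Two SGA-7 domains (6 months) and one EFS item (past year) look back further than the 12-week treatment, so they can move with no on-study change and mislead the within-arm change named in 3.4.1

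*Protocol*

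**What the plan says.** Section 3.1 states: "The treatment period is 12 weeks". It also sets the scoring times: "At 0, 12th and 24th week, quality of life score, nutrition evaluation, diet status and gastrointestinal symptom score of patients will be evaluated".

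Section 3.4.1 names as primary "Changes of nutritional status from the baseline to the end of treatment and differences between the intervention group and the placebo group", and adds: "Nutritional status of the patient is defined as the results of physical examination and SGA-7 rating scale". The quality-of-life primary outcome is worded in the same way and includes the "kidney disease life quality scale (TM-SF36) and enervation frailty scale (EFS"), together with the GSRS.

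The forms in the appendices set the reference periods:

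- Appendix A (SGA-7), weight domain: "Change of Weight (Measured in % compared to the weight 6 months earlier").
- Appendix A (SGA-7), daily living domain: "Ability of Daily Living (Compared to 6 months ago").
- Appendix D (EFS), first general-health question: "How many times did you hospitalize in the past year", scored 0 to 2.

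The other four SGA-7 domains (diet, gastrointestinal symptoms, metabolic stress, physical examination) and the other ten EFS items carry no 6- or 12-month window. Appendix A tells the rater to give the SGA-7 total as an overall judgement from 1 to 7 and not to average the items. Nothing in the protocol changes the reference periods of the three dated items at week 12 or week 24.

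**The concern.** An item that compares today with a date before randomisation does not measure change since randomisation. As follow-up proceeds its reference point moves forward, so an old weight loss or hospital stay can drop out and the score can improve with no on-study event. Conversely, a patient who gains weight on study can still be scored as a substantial loser.

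This matters because 3.4.1 names change from baseline as a primary quantity beside the between-arm difference. Drift in the dated items can pass for a response within an arm. It also adds variance to the between-arm comparison, in a trial planned at 30 per group.

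**Working it through.** **Inputs.** Treatment of 12 weeks and scoring at weeks 0, 12 and 24 (3.1); look-backs of 6 months, about 26 weeks, and one year, about 52 weeks (Appendices A and D). Baseline scoring is taken as week 0. The protocol gives no figure of its own on this point to reproduce.

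**Step 1: where the look-back falls at week 12.**

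- 6-month items: 12 - 26 = week -14. Pre-treatment share 14/26 = 54%, on treatment 12/26 = 46%.
- One-year item: 12 - 52 = week -40. Pre-treatment share 40/52 = 77%, on treatment 12/52 = 23%.

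**Step 2: how much of each scale is affected.**

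- SGA-7: 2 of 6 domains (2 of 8 if fat, muscle and edema are counted separately). Their share of the total cannot be computed, because the total is a global rating.
- EFS: the item maxima are 2+2+2+2+2+1+1+1+1+1+2 = 17 over 11 items. The dated item carries 2/17 = 11.8%.

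**Step 3: can the items move with no on-study change?** Appendix A holds two weight-scoring tables that disagree. That is a separate matter to be reconciled; both results are shown where they differ.

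- *False improvement.* A patient loses 8% between weeks -26 and -14 and is then stable. At week 0 the 6-month loss is 8%, scored 4 on the assessment-form table or 3 on the table after the result sheet. At week 12 the reference is week -14, the loss is 0% and the score is 7. The item rises by 3 or 4 points with no on-study weight change.
- *Masked improvement.* Weights are 60 kg at week -14, 54.6 kg at week 0 and 55.2 kg at week 12. On-study change is 55.2/54.6 - 1 = +1.1%. The item sees 55.2/60 - 1 = -8%, scored 4 or 3.
- *EFS.* Three admissions at weeks -50, -46 and -42 and none later. The item scores 2 at week 0 and 0 at week 12. An EFS of 8 (mild weakness) would become 6 (vulnerable).

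These are changes in single items. The EFS change carries directly into the total; the SGA-7 change need not.

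**Step 4: group B at week 24.** The 6-month reference is 24 - 26 = week -2. The interval holds 12 weeks on product, 12 on placebo and about 2 before treatment, so the weight item cannot isolate the product period. Under 3.3.3.4 group A has left by then, so weeks 13-24 have no concurrent control.

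**Step 5: would re-anchoring the SGA-7 weight item to baseline solve it?** Take a steady loss of 4% per 12 weeks. The 26-week loss at baseline is 1 - 0.96^(26/12) = 8.5%, scored 3 on the table after the result sheet. Scored against week 0 on the same bands, the week-12 loss is 4%, scored 5. That is a false gain of 2 points at an unchanged rate of loss. As written, the item stays at 3.

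**The case against.** A reader might infer that the week-12 SGA-7 and EFS scores mostly describe time before treatment. The documents do not support that. At least 15 of 17 EFS points and 4 of 6 SGA-7 domains have no such window, and the SGA-7 total is a clinical judgement. The rater also sees recent information: the form records dry weight 2 months ago, which at week 12 falls at about week 3, and some weight anchors refer to recent trend.

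A reader might also infer that the treatment comparison is biased. It is not: under concurrent 1:1 randomisation the pre-randomisation reference and the drift are equal in expectation in both arms. Nor is the 54% a fraction of signal lost. The weight item compares two points, and week-12 weight carries the whole effect of treatment. The cost is extra variance.

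Further points on the other side:

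- A 2-point EFS fall through drift needs at least three admissions that all leave the window between weeks -52 and -40, and none afterwards. With a steady admission rate the expected group drift is zero.
- Daily-living response options largely describe present state, so the weight and hospitalisation items carry most of the case.
- Section 5.4 refers to standard operating procedures for the scales. These are not shown and might address the reference period.
- Section 3.6 calls the trial exploratory, section 3.7 says the scales are widely used in hemodialysis patients, and using them unmodified is defensible. GSRS (past week) and the TM-SF36 items that state a period (past 4 weeks) do not share the problem.

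All of this stands, and it confines the point to three items. It does not protect within-arm change, which 3.4.1 names. Group B's weeks 13-24 would be uncontrolled whatever the look-back; the 6-month reference then adds placebo and pre-trial time to the item.

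**Conclusion.** The point holds for the three dated items. At week 12 their look-back is 54% (SGA-7 weight change and daily living) or 77% (EFS hospitalisation) pre-treatment, and they can move with no on-study change: by 3 or 4 item points in the SGA-7 weight example and by up to 2 of 17 EFS points in an extreme case. The effect on the SGA-7 total cannot be quantified.

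For the between-arm comparison the consequence is added noise. For within-arm change it is a real risk of misreading, greatest in group B at week 24. The conclusion assumes that 6 months is about 26 weeks, that baseline is scored at week 0, that the forms are applied as printed, and that no unseen scoring procedure alters the reference periods. It is a modest weakness in a primary outcome, and cheap to contain.

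**What to change.** Keep the standard SGA-7 and the 17-point EFS as the primary scores. Re-anchoring SGA-7 is not recommended as the primary approach, because it can create a false improvement of its own.

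- In 3.4.1 and 3.8, state that the treatment conclusion rests on the between-arm comparison of week-12 scores, adjusted for the baseline score.
- State that within-arm change, including group B over weeks 13-24, is descriptive and will not be read as a treatment effect.
- Add two supportive analyses: EFS without the past-year hospitalisation item (17 - 2 = 15 points), and on-study percent change in dry weight from baseline, compared between arms and not scored on the 6-month bands.

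No new data are needed. The SGA-7 form already records current dry weight each time it is completed, section 3.3.3.1 records it at screening, and EFS is scored item by item. The cost is a few sentences and a little extra analysis. The 15-point EFS departs from the standard form, which is why it stays supportive.
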